The design of this study is a randomized experimental trial. The procedures involved in this study will first include obtaining the individual's consent to participate. Incentive spirometry is a standard of care that has been proven to improve deep breathing for patients. FVC/FEV₁ measurements are not always routinely done at this site but has been proven to be an indicator in respiratory deterioration in this population. Enrollment of each subject will be on a one to one basis for control and experimental groups. The trial will be randomized to reduce bias by randomly selecting patients between control and experimental groups by alternating every other patient receiving the treatment. Height, sex, ethnicity, and age will be accounted for as well to calculate the percent predicted FVC/FEV_1 to reduce statistical error. Enrollment will be based on patient consent. After enrollment into the study after admission to the hospital, baseline values of incentive spirometry (IS) and spirometry will be done. The patient will then be placed in the experimental or control group after being assigned a group via envelope randomization. If the patient is under experimental, they will receive a splinting device for treatment. Control groups will receive standard of care treatment without the splinting device. Continued analysis of IS and FVC/FEV₁ will occur over three days, and a final collection prior to discharge. Discharge planning will be coordinated with respiratory therapy, so the patient does not go home without completing the survey and final analysis. The patient satisfaction survey will be a paper survey administered to the patient. Patient identifying information will not be present on this form to maintain confidentiality. The patient will be asked if they would like to complete the form and that it is an anonymous short survey to help with identifying how the patient felt about the research. The subject will only be enrolled in the study for the duration of their hospital stay as an inpatient. There will be no follow-up after discharge, and any patients who are discharged without completing the final analysis will be omitted from the study.

11) Data Analysis Plan

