Data analysis will include a two-tailed t-test to account for significance between control and experimental groups. This will be done with both incentive spirometry and FVC/FEV₁. Correlations will be made with time to ambulation and length of stays, as well as injury severity score. Graphic representation of trends will also be used to demonstrate differences between the groups. Qualitative analysis will include providing averages from the questionnaire using a Likert scale. These averages will be used to determine whether the population felt the device provided any help with their chest trauma. Number of subjects was based on a power analysis

using FVC/FEV₁ as the primary variable. Previous literature suggests a standard deviation of approximately 0.20-0.60 for FVC/FEV₁ values. SD was set at 0.40. Unilateral control was estimated to be 50% of predicted values (FVC/FEV₁) due to the nature of the injury, set at approximately 1.50L, with bilateral set at approximately 1.35L. Unilateral experimental group means were increased by 20% of predicted values to 1.80L, and bilateral to 1.50L. The required sample size to achieve 80% power to detect difference between splint and control groups is 104, with each group requiring 26 subjects each. Power calculations were performed in R version 4.0.0 with the pwr2ppl package, using the anova2x2 function. Number of subjects to be used are 150 to account for withdrawals, incomplete data sets, extraneous results, etc. This is a single site study.

Patient satisfaction surveys will use a numbered Likert Scale. The averages of each answer will be used to reinforce the efficacy of the device and correlate to primary data. Randomization will occur by experimenter-blinded envelope randomization.

12) Provisions to Monitor the Data to Ensure the Safety of Subjects

Subjects will be monitored for the duration of their stay by all staff members, and any adverse events related to the device itself will be reported accordingly. This device claims minimal risk to patients due to its unrestrictive and non-invasive nature but will be monitored by investigators for any adverse effects. **The Data Safety Monitoring staff will review all documentation accordingly at least quarterly.**

13) Withdrawal of Subjects

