Subjects may voluntarily withdraw from the study at any time during their admission. Subjects may be withdrawn from the study if they are discharged prior to final analysis, deterioration of health rendering them incapable of participating in research, or verbal authorization to remove them from the study. Subjects may be removed in the case that the protocol needs to be revised due to an unforeseen adverse event that would exclude them from the study. All data will be retained unless specified by the subject up to the required date.

14) Risks to Subjects

The risk to subjects is extremely minimal. Chest trauma is consistently treated with incentive spirometry and monitored with FVC/FEV_1 percent predicted values. There is very little risk to the patient with these procedures, and only some discomfort and pain from the rib fractures may be associated. The difference is the addition of the splinting device. Splinting devices are routinely used in the hospital for open heart patients and produces no associated risk to those patients. It is unlikely that this splinting device will produce any adverse events. The device is unrestrictive and only splints the chest when the patient wants it to. The only

CHI Institute for Research and Innovation

potential risks are some discomfort, and an unknown allergy to the urethane coated polyester fabric on the device.

15) Potential Benefits to Subjects

Potential benefits to the subjects are unknown currently.

16) Sharing of Results with Subjects

Specific study results will not be shared with subjects

17) Setting

Potential subjects will be recruited at Penrose Hospital in Colorado Springs, CO.

18) Resources Available

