The primary non-English speaking subject will be Spanish in this region. The hospital has access to translators that can translate for a patient if this were to be necessary. A short form will be used to obtain consent if a non-English speaking patient is enrolled in the study.

Cognitively Impaired Adults/Temporary or Permanent Lack of Capacity to Provide Informed Consent

The process to determine whether an individual can give verbal consent will be conducted by determining if they are oriented to person, place, and time. If this changes after enrollment and the patient is unable to make decisions for themselves, the dedicated medical power of attorney for that patient will be consulted. The use of this device requires intact cognition and may cause them to be omitted from the study in this case.

25) Process to Document Consent in Writing

Informed consent will be obtained in the patient room within the first 24 hours of admission. This will be a paper consent form and will be signed by the subject if the subject decides to be included in the study. All inclusion criteria must be met. The informed consent follows the CIRI template and outlines all procedures and risks associated with the study. Informed consent will be retained for the duration of the study and thereafter in accordance with regulations. Please see the informed consent for all information given to the patient.

26) Drugs or Devices

The splinting device will be primarily made of a urethane coated polyester fabric with anti-microbial additives which is soft, pliable, and stretchable. The device will be stored within the respiratory therapy equipment storage room at Penrose hospital and the research team will be notified by the Trauma team or respiratory therapy when a subject is admitted to the hospital who meets inclusion criteria for the study.

The FDA was contacted regarding the IDE Approval Process. Based on the response from the encounter with the FDA, that during the approval process with the IRB, the governing body of the IRB would deem the device as Significant or Non-Significant. The claim of the Duracore

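### Sections 10, 13 and 24 let assigned patients leave the comparison because of how they fared, and no rule says how their retained data are analysed

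*Combined protocol and SAP*

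**What the plan says.** Four rules govern patients who have already been assigned.

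- **Section 13, deterioration.** A subject may be withdrawn for "deterioration of health rendering them incapable of participating in research".
- **Section 13, protocol revision.** "Subjects may be removed in the case that the protocol needs to be revised due to an unforeseen adverse event that would exclude them".
- **Section 10, final measurement.** "any patients who are discharged without completing the final analysis will be omitted from the study". Section 13 lists the same situation only as a reason for which a subject may be withdrawn.
- **Section 24, loss of capacity.** If orientation is lost after enrolment, "The use of this device requires intact cognition and may cause them to be omitted from the study in this case".

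Against these, section 13 also states: "All data will be retained unless specified by the subject up to the required date".

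Section 11 plans a two-tailed t-test on incentive spirometry and FVC/FEV₁, with correlations for time to ambulation and length of stay. Neither it nor any other section defines an analysis population, says how retained data are used, or provides for data collection after removal. Section 33 requires missing CRF items to be accounted for but gives no analysis rule for them.

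**The concern.** Randomised arms are comparable only while the patients assigned to them are the ones compared. Each of these rules acts after assignment, and each can depend on how the patient did or on which arm the patient was in.

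For lung capacity the link is direct. Section 10 justifies following FVC/FEV₁ on the ground that it "has been proven to be an indicator in respiratory deterioration in this population", and section 13 then allows withdrawal of patients whose deterioration is incapacitating. If the splint prevents such deterioration, leaving these patients out hides benefit. If it contributes to it, leaving them out hides harm.

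For length of stay and time to ambulation the loss is also unnecessary. Section 3 takes ambulation from the first physical therapy assessment, and length of stay is a hospital record. Neither needs the patient to perform a breathing test, yet a patient omitted from the study is lost to both. Length of stay is in the study hypothesis.

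**Working it through.** **1. How the rules combine.** A patient withdrawn for incapacitating deterioration will usually have no pre-discharge spirometry. On discharge, that patient meets the section 10 condition, which is the only one of the four worded as certain rather than permitted. Section 13 keeps the data, section 10 takes the patient out of the study, and nothing says which governs the analysis. The same rule can also catch a patient who goes home quickly before the last test, so the selection need not run in one direction.

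**2. The plan's own figure.** Section 6 gives SD 0.40 and means, in litres, of 1.50 (control) and 1.80 (splint) for unilateral fractures, and 1.35 and 1.50 for bilateral.

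- Average splint effect = [(1.80 − 1.50) + (1.50 − 1.35)] / 2 = (0.30 + 0.15) / 2 = 0.225 L.
- Main effect in a 2×2 ANOVA with 26 per cell: noncentrality = 104 × (0.225/2)² / 0.40² = 8.23 on 1 and 100 degrees of freedom. At a two-sided alpha of 0.05 (assumed; none is stated) power is 0.811. With 25 per cell it is 0.795.

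The stated 104 is therefore reproduced. Enrolling 150 leaves room for 150 − 104 = 46 patients (30.7%) not analysed, so losses of the size considered below would not stand out.

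**3. Shift from removing deteriorated patients.** Let *r* be the share removed in an arm and *d* their deficit relative to those who remain. The full-arm mean is the remaining mean minus *r* × *d*, so removal raises the arm mean by *r* × *d*. With the same *d* in both arms, the estimated splint effect changes by (*r* splint − *r* control) × *d*. The documents give neither *r* nor *d*; the values below are assumptions.

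| Removed, control v splint | *d* = 0.5 L | *d* = 0.8 L | Share of 0.225 L |
|---|---|---|---|
| 8% v 2% | −0.030 L | −0.048 L | 13% to 21% |
| 6% v 3% | −0.015 L | −0.024 L | 7% to 11% |
| equal rates | 0 | 0 | 0 |

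A minus sign means the benefit is understated. With the rates exchanged between arms, the same amounts overstate it.

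**4. An upper bound under no true effect.** Assume normal data, SD 0.40, 75 per arm, removal strictly of the lowest values, and none of the retained readings used. Removing the lowest share *p* raises an arm mean by 0.40 × φ(z_p) / (1 − *p*), which is 0.078 L at 10% and 0.043 L at 5%. Removing 10% of splint and 5% of control patients shifts the difference by 0.078 − 0.043 = 0.035 L in favour of the splint. By simulation, the nominal 5% test then rejects about 12% of the time. With 5% removed in each arm the shift is about zero and the rejection rate about 7%.

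No similar figure can be given for length of stay or ambulation, because the plan states no means or SDs for them.

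**The case against.** The strongest reply is that section 13 retains the data and does not itself exclude anyone from the t-test, so the plan is silent rather than wrong. That stands for section 13 read alone. It does not stand for the plan as a whole, because section 10 does omit patients and a withdrawn patient will usually meet its condition.

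Three further points stand and limit the concern. The deterioration clause covers only patients who can no longer take part; someone whose FVC falls but who can still perform the test stays in. An effort test that cannot be done is missing under any rule. The illustrated shifts of 0.030 to 0.048 L are also modest beside the standard error at 52 per arm, 0.40 × √(2/52) = 0.078 L, being about 0.4 to 0.6 of it.

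A reader might go further and infer that harmed patients vanish from the safety results. The documents do not support that:

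- Section 12 says "any adverse events related to the device itself will be reported accordingly", with no exception for removed patients, and section 26 requires daily monitoring of device users.
- The revision clause can operate only after an event has been recognised, so it cannot conceal that event. It is permissive, and it covers whoever the revised protocol would exclude, possibly in both arms, not specifically those harmed.
- Fabric allergy is not an example of the clause, which concerns unforeseen events; section 14 names that allergy in advance.
- The section 14 statement "It is unlikely that this splinting device will produce any adverse events" is a prospective risk assessment, not a result that removals could protect.

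**Conclusion.** The concern holds for efficacy. Following the plan as written can select the lung-capacity comparison by outcome, and can discard length of stay and time to ambulation for patients in whom both could still be collected. It does not hold as a claim that observed adverse events are dropped.

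The direction and size of the bias cannot be determined from the documents. The range of 0.03 to 0.05 L (13% to 21% of the planned effect) rests on assumed removal of 8% in control and 2% in splint, and on an assumed deficit of 0.5 to 0.8 L relative to remaining patients. Smaller imbalances give less, and equal rates with equal deficits give about zero. The defect to correct is that data are retained under section 13 while patients are omitted under sections 10 and 24, with no analysis set to settle which applies.

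**What to change.** Amend sections 10, 11, 13 and 24 together; changing section 13 alone would leave the operative omission in place.

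1. State that all assigned patients are analysed in the arm to which they were assigned, unless the subject withdraws permission to use the data. Replace the omission wording in sections 10 and 24 accordingly.
2. State that a change in eligibility made after assignment does not remove a patient from the analysis, whatever is decided about device use.
3. Use readings taken before withdrawal. Where consent allows, continue to collect length of stay, time to ambulation and adverse events from the chart.
4. Record a missed effort test as not done, with the reason, and report removals by arm and reason.
5. Add one supporting rank-based comparison of lung capacity in which a reading missing because of deterioration takes the lowest rank. Name its time point, since the plan does not choose among the three days and the pre-discharge test.

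The cost is protocol wording, one reason code on the CRF, some continued chart review and one extra test. The sample size need not change. The one drawback is that the worst-rank result is not in litres, so it supports the main comparison rather than replacing it.

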Title: Effects of using the Duracore Splinting Device on Patient Outcomes Related to Chest Trauma

Protocol Version Number: 3

Protocol Version Date: 12/8/2020

CHIRB IRBNet ID: 1517921-3

1) Investigators

Principal Investigator

[name] Title: Registered Respiratory Therapist Department: Respiratory Therapy [contact] Email: [contact]

Co-Investigator:

[name] Title: Registered Respiratory Therapist Department: Respiratory Therapy [contact] Email: [contact]

Co-Investigator:

[name] Title: Registered Respiratory Therapist Department: Respiratory Therapy [contact] Email: [contact]

Co-Investigator:

[name] II, M.D. Title: Surgical Trauma Physician Department: Trauma Services Email: [contact]

2) Funding Source

Financial funding was obtained by grants from local agencies through application processes, along with interviews and assessment of the medical device. The first grant was obtained through the Southern Colorado Society of Respiratory Care in hopes to obtain better choices for treatment for patients with rib fractures. Additional funding was provided by the Penrose Foundation as well.

3) Objectives and Hypothesis(es)

The purpose of this study is to use the Duracore patient operated torso splinting device for patients with chest trauma, including rib fractures, to improve deep breathing and help with reduced hospital length of stays (LOS). The hypothesis of this study is that the use of the Duracore splinting device will reduce hospital length of stays and improve patient lung capacities over the course of admission following chest trauma.

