The study will use a randomized-experimental design and will be randomized via envelope randomization, with experimenters being blinded. A total of 104 patients, 26 in each group, will undergo initial incentive spirometry and force vital capacity (FVC) and FEV₁ tests. Groups will consist of a control versus experimental group, stratified into bilateral and unilateral rib fractures. Three days' worth of data will be collected for each of the tests and will also be collected 24 hours prior to discharge. Length of stays will be compared for experimental and control groups, as well as time to ambulation (collected from the first physical therapy assessment). Injury severity score will also be collected to determine any correlation by severity of injury. Patient satisfaction surveys for the device will also be collected to determine if the patients feel a difference with the device.

4) Background/Scientific Rationale and Significance

Little research as been conducted to determine the significance of a splinting device used in patients with chest trauma, and it is still uncertain whether these devices improve overall patient outcomes. Contradicting studies with similar experimental designs show either some significance (p-value) or insignificance in pulmonary function pre- and post-treatment. This gap in current knowledge leaves room for concern in whether the patient truly benefits from a splinting device in this type of injury. Changes in percent predicted FVC/FEV₁ ratio in this patient population are not readily demonstrated in most of these studies, as well as differing length of stays. This study will contribute to this base of knowledge by determining the effects of the Duracore splinting device on this patient population using the objectives.

5) Inclusion and Exclusion Criteria

Inclusion:

- Adult patient admitted to the trauma service at Penrose Hospital
- Willing and able to comply with all requirements of the study
- Active diagnosis of rib fractures
- Male or female ages 18 and older
- Able to provide written informed consent to participate in the study
- Must be physically able to don and use the splinting device independently without assistance

Exclusion:

- <18 years old
- History of pulmonary disease, lobectomy, or lung transplant
- Current smoker of tobacco products >5 years
- Diagnosis of flail chest

- Pregnant Women
- Prisoners
- Cognitively Impaired; must be alert and oriented x 3

6) Number of Subjects

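### The loss-of-orientation rule gives splint patients an extra, discretionary route out of the study after assignment, so the length-of-stay comparison could be biased towards the splint

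*Combined protocol and SAP*

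**What the plan says.** Section 24 (Consent Process, under the heading on cognitively impaired adults and lack of capacity) deals with a patient who was oriented at consent and later is not. The holder of the patient's medical power of attorney is then to be approached, and no arm is named. The section adds: "The use of this device requires intact cognition and may cause them to be omitted from the study in this case".

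Section 10 (Procedures Involved) places group assignment after consent and baseline testing, and states: "Control groups will receive standard of care treatment without the splinting device".

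Section 13 (Withdrawal of Subjects) has a separate ground that names no arm: "deterioration of health rendering them incapable of participating in research". It also says that data are kept unless the subject specifies otherwise, but not that the data of withdrawn patients are analysed.

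Section 5 applies an orientation criterion to everyone at entry: "Cognitively Impaired; must be alert and oriented x 3". Section 3 makes length of stay part of the hypothesis, namely that "the use of the Duracore splinting device will reduce hospital length of stays", and says that stays will be compared between the groups. No section defines an analysis set.

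**The concern.** Removing patients after assignment is harmless to the comparison only if it takes the same kind of patient from both arms. In section 24 the one reason given for omission is that the device needs intact cognition. A disoriented control has no device, so that reason cannot be applied to a control. The rule is also discretionary and gives no criteria. Section 26 has device users monitored daily for adverse effects, so staff will know who has a splint.

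Patients who become disoriented during a trauma admission may well stay longer; the documents do not say so. If they do, removing more of them from the splint arm lowers that arm's mean stay without any effect of the device. The error would point the same way as the trial's hypothesis. Lung volumes could be affected in the same way, but the documents give nothing from which to size that.

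**Working it through.** **The plan's own figure.** The stated sample size reproduces. The splint main effect is ((1.80 + 1.50) − (1.50 + 1.35))/2 = 0.225 with SD 0.40. With 26 per cell (104 in total) the noncentrality is 104 × (0.225/2)² / 0.40² = 8.23, which gives 81.1% power; 25 per cell gives 79.5%. Alpha is not stated, so 0.05 is assumed. This figure concerns FVC/FEV₁. The plan gives no figure for length of stay, so the rest is an illustration.

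**Grounds for removal after loss of orientation, by arm.**

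| Ground | Splint | Control |
|---|---|---|
| Section 24: device needs intact cognition | applies | stated reason cannot apply |
| Section 13: deterioration of health | applies | applies |
| Section 10: discharged without the final assessment | applies | applies |

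The difference between the arms is the first row.

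**Effect on mean stay.** Let f be the share who become disoriented (equal in both arms), D their extra days, and r the share of them removed from an arm. The mean stay of the patients left in that arm exceeds the usual mean by D·f(1 − r)/(1 − f·r). The false difference is this quantity for splint minus that for control.

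Assumed inputs, none of them in the documents: no true effect; usual stay gamma with mean 5 and SD 2.5 days; f = 5%, 10%, 15%; D = 5 or 2 days. The arm size of 52 is 2 × 26 from the plan.

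- Splint only, D = 5: −f·D = −0.05 × 5, −0.10 × 5, −0.15 × 5 = −0.25, −0.50, −0.75 day.
- All disoriented splint patients and half of the disoriented controls, D = 5: −5 × 0.025/0.975, −5 × 0.05/0.95, −5 × 0.075/0.925 = −0.13, −0.26, −0.41 day.
- Half of the disoriented splint patients and no controls, f = 10%, D = 5: 5 × 0.05/0.95 − 0.50 = −0.24 day.
- Splint only, D = 2: −0.10, −0.20, −0.30 day.
- Equal removal: 0.

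**Chance of a false benefit.** This is the share of simulated trials with two-sided p < 0.05 in the splint's favour, by pooled t-test, with at least 8,000 trials per scenario. The nominal rate is 2.5%.

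| Scenario | f = 5% | f = 10% | f = 15% |
|---|---|---|---|
| Splint only, 5 extra days | about 7% | about 14% | about 24% |
| Half of controls also removed, 5 extra days | about 4% | about 7% | about 10% |
| Splint only, 2 extra days | about 4% | about 6% | about 8% |
| Equal removal | about 2.6% | about 2.6% | about 2.6% |

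With half of the splint patients removed, no controls, f = 10% and 5 extra days, the rate is about 6%.

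**Different assumptions.** With 75 per arm (150/2), usual stay mean 5 and SD 3.2 days, f of 5% to 15% and D of 2 to 6 days, splint-only removal gives a false reduction of 0.1 to 0.9 day. The two-sided rejection rate is then 5.3% to 31.3%, against 5% nominal. At 10% and 4 days it is 0.4 day and 11.3%. Equal removal again gives about 0 day and about 5%.

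**The case against.** The strongest reply is that the documents do not make removal one-sided. Section 24 says that patients may be omitted, not that they will be. Its trigger is any enrolled patient who loses capacity, whatever the arm. The deterioration clause in section 13 can plainly cover a disoriented control. A reader might infer that such controls stay in while splint patients leave, and hence that length of stay is biased. The text does not support that: one-arm removal is the extreme case, and relaxing a single input at 10% disoriented brings the false-benefit rate down from about 14% to about 6% or 7%. This part of the reply stands. What it does not remove is the extra ground in the splint arm, the absence of criteria for using it, and the lack of any statement that omitted patients are analysed.

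Two further points stand. Section 11 assigns the t-test to incentive spirometry and FVC/FEV₁ and speaks of correlations for length of stay, so the rejection rates assume a test that the plan does not clearly specify; the shift in means does not depend on it. Also, the withdrawn patients' data are kept under section 13, so the remedy needs nothing new, although keeping data is not the same as analysing them.

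A reader might also see a second one-sided rule in section 13: "Subjects may be removed in the case that the protocol needs to be revised due to an unforeseen adverse event that would exclude them". That sentence names neither arm nor device, and it works only through a protocol revision, which needs IRB approval. It would be one-sided only if the event were device-related, which is conjecture, so it is not part of this point.

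Finally, this can be called one instance of a wider gap, since section 10 also provides that "any patients who are discharged without completing the final analysis will be omitted from the study". That is fair, but section 10 applies to both arms by its wording. The section 24 reason does not.

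**Conclusion.** The concern holds as a risk. Sections 13 and 24 are not reconciled, the device-based reason can apply only to splint patients, and no section keeps omitted patients in the length-of-stay comparison. Length of stay could therefore be biased in favour of the splint; the documents do not show that it will be.

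The size rests on three unknowns: how many patients become disoriented, how much longer they stay, and how unequally the rule is applied. With 52 per arm and 5% to 15% disoriented, the false reduction runs from about 0.1 day (2 extra days, 5% disoriented) to 0.75 day (5 extra days, 15% disoriented) when removal is from the splint arm only. It is nil when removal is equal, and small if disorientation is rare. The change is worth making because it costs little and removes a bias that would favour the hypothesis.

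**What to change.** Reconcile sections 13 and 24 so that the rule on staying in the study after loss of orientation is the same in both arms and does not rest on device use. State that a patient who stops the device or further testing is not thereby omitted from the analysis. Charted length of stay, time to ambulation and readings already taken are analysed in the assigned arm, unless permission to use the data is withdrawn. Word the omission sentence in section 10 to match, or the same patients could be lost by that route. Report the number affected and the reason, by arm. Clinical decisions on device use and testing stay with the investigators; the change concerns only who is analysed.

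The cost is a few sentences in an amendment. Length of stay and time to ambulation come from records made during the admission, so no new visits are needed, and the sample size of 104 is unchanged. The downside is slight dilution of the estimated effect, because splint patients who could no longer use the device remain in their arm.
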